### **12.1.2 Serious Adverse Events**

A serious adverse event (SAE) is an AE that meets one or more of the following criteria:

- Results in death.
- Is life-threatening (ie, a subject is at immediate risk of death at the time of the event, not an event where occurrence in a more severe form might have caused death).
- Requires hospitalization or prolongation of existing hospitalization.
- Results in persistent or significant disability or incapacity.
- Is a congenital anomaly or birth defect.
- Is an important medical event that may jeopardize the subject or may require a medical or surgical intervention to prevent one of the outcomes listed above.

Examples of such medical events include allergic bronchospasm requiring intensive treatment in an emergency room or at home, blood dyscrasias or convulsions that do not result in inpatient hospitalization.

The term "severe" is often used to describe the severity of a specific event (as in mild, moderate, or severe myocardial infarction) (see Section 12.3 Collection and Recording Adverse Events, p54); the event itself, however, may be of relatively minor medical significance (such as severe headache). This is not the same as "serious," which is based on subject/event outcome or action criteria usually associated with events that

pose a threat to a subject's life or functioning as defined by the criteria above.

During the study, if a subject has a hospitalization or procedure that was scheduled before the study entry, ie, before informed consent for an event/condition that occurred before the study, the hospitalization is considered a therapeutic intervention and not the result of a SAE. However, if the event/condition worsens during the study, it should be reported as an AE (or SAE, if the event/condition results in a serious outcome such as prolongation of hospitalization).

## **12.2 Objective Findings**

Clinically significant abnormal objective findings (eg, clinical laboratory value, ECG value, and physical examination observation) will also be recorded as AEs. When a clear diagnosis is available that explains the objective findings, this diagnosis will be recorded as the AE, and not the abnormal objective finding (eg, viral hepatitis will be recorded as the AE, not transaminase elevation). If a definite diagnosis is not available, then record the sign (eg, clinically significant elevation of transaminase levels) or symptom (eg, abdominal pain) as the AE.

Clinical laboratory test results will be reviewed by the Investigator. The Investigator must determine the clinical significance of all out of range values. Clinical laboratory test with possibly drug-related or clinically relevant abnormal values of uncertain causality may be repeated. Any abnormal values that persist should be followed at the discretion of the Investigator. Laboratory reports will be initialed and dated by the Investigator.

All ECG tracings at the study center and ECG over-read reports by the central ECG reader will be reviewed by the Investigator. The Investigator must determine the clinical significance of all abnormal ECGs. An ECG with possibly drug-related or clinically relevant abnormal findings of uncertain causality may be repeated. Any abnormal ECGs that persist should be followed at the discretion of the Investigator. ECG tracings will be initialed and dated by the Investigator.

## **12.3 Collection and Recording Adverse Events**

All AEs will be, in principle, followed up until resolution, stabilization of the condition, the event is otherwise explained, or the subject is lost to follow-up. All AEs must be collected and recorded in the subject's study records/source documents, in accordance with the Investigator's normal clinical practice. AEs will be recorded in the CRFs

from the beginning of the study treatment in the washout phase until the follow-up visit.

Each AE is to be evaluated for duration, severity, seriousness, action taken with the study treatment, outcome, and causal relationship to the study treatment. If any AEs related to skin disorders occur at the application site, the Investigator will record the location (the back, chest or abdomen) of AEs occurrence.

Definitions for severity, action taken with the study treatment, outcome, and causal relationship to the study treatment are presented below.

**The severity of AE:**

- Mild – Ordinarily transient symptoms that do not influence performance of subject's daily activities. Other treatment is not ordinarily indicated.
- Moderate – Marked symptoms sufficient to make the subject uncomfortable. Moderate influence on performance of subject's daily activities. Other treatment may be necessary.
- Severe – Symptoms cause considerable discomfort. Substantial influence on subject's daily activities. May be unable to continue the study, and other treatment may be necessary.

**The action taken with the study treatment:**

**During the washout phase**

- Drug Withdrawn – Study drug stopped permanently.
- Dose Not Changed.
- Not Applicable.

**During the double-blind treatment phase**

- Drug Withdrawn – Study drug stopped permanently.
- Dose Not Changed.
- Not Applicable.

**During the open-label treatment phase**

- Drug Withdrawn – Study drug stopped permanently.
- Dose Reduced.
- Dose Increased.
- Dose Not Changed.
- Not Applicable.

**The outcome of the AE:**

- Recovered/Resolved.
- Recovering/Resolving.
- Not Recovered/Not Resolved.
- Recovered/Resolved with Sequelae.
- Fatal.
- Unknown.

**The causal relationship of the AE to the study treatment:****Not related**

- Not related – Improbable temporal relationship and is plausibly related to other drugs or underlying disease.

**Related**

- Possible – occurred in a reasonable time after study drug administration (application), but could be related to concurrent drugs or underlying disease.
- Probable – occurred in a reasonable time after study drug administration (application), is unlikely to be attributable to concurrent drugs or underlying disease, and there is a plausible mechanism to implicate the study drug.
- Definite – occurred in a reasonable time after study drug administration (application) and cannot be explained by concurrent drugs or underlying disease. The adverse event should respond to dechallenge/rechallenge, however, this is not mandatory before assigning a definite causality.

The Medical Monitor is the initial contact person outside Japan for protocol related questions or discussion of AEs. In Japan, the Sponsor or the designees are the contact persons. The contact information as well as other emergency contact information can be found in Table 1 and 2 Emergency Contact Information (p3).

**12.4 Immediately Reportable Events**

The following medical events must be immediately reported to the Sponsor/CRO:

- SAE
- Pregnancy

Emergency contact information can be found in Table 1 and 2 Emergency Contact Information (p3).

**12.4.1 Serious Adverse Event**

If the Investigator or staff of study centers becomes aware of SAE that occurs in a

study subject from the beginning of the study treatment in the washout phase until the follow-up visit, this must be reported immediately to the Sponsor/CRO whether considered related or unrelated to the study drug. SAEs occurring from the beginning of the study treatment in the washout phase until the follow-up visit must be recorded in the CRFs.

Following the end of subject participation in the study, the Investigator should report SAEs “spontaneously” to the Sponsor/CRO if considered at least possibly related to the study drug.

SAEs will be followed until resolution, loss to follow-up, stabilization of condition, or the event is otherwise explained.

The Investigator must inform the Sponsor/CRO (Table 1 and 2 Emergency Contact Information) of any SAEs that occur during the course of the study within 24 hours of the Investigator becoming aware of the SAE.

The SAE report should include the following information:

1. Study number (D4904020)
2. Subject number
3. Sex
4. Date of birth
5. Name of investigator and study site
6. Nature of SAE
7. Criterion for classification as “serious”
8. Date of initial administration of the study drug
9. Start date of SAE
10. Causality (if sufficient information is available to make this classification)
11. History of any ADRs
12. Relevant special conditions of the subject
13. History of the current disease and treatment for the disease
14. Details of the SAE
15. Treatment for the SAE
16. Details of study treatments
17. Details of concomitant medications
18. Details on course of the SAE
19. If the subject died, date of death, cause of death, relationship between the SAE

and death, anatomic findings (if available)

As a minimum requirement for the first report, information on items 1 to 10 described above should be provided directly or in a form of a report, by facsimile, or by telephone. The Principal Investigator should report available information in writing within 7 calendar days after the first reporting (this procedure is not mandatory in the case that the Principal Investigator has already submitted the first report, including all necessary information listed above). The Principal Investigator should report other necessary information not included in the first and second reports in writing as it becomes available. The Sponsor/CRO may request additional information, if deemed necessary.

The Sponsor or designee will promptly notify all study centers and Investigators of a SAE that is determined to be expedited to the Regulatory Authorities in accordance with applicable law(s) and regulation(s). These SAEs must be promptly reported to the Institutional Review Board (IRB)/IEC by the Principal Investigator or the appropriate person at the study center. In Japan, these SAEs must be promptly reported in writing to the head of the study center by the Principal Investigator.

#### **12.4.2 Pregnancy**

Pregnancies that occur from the beginning of the study treatment in the washout phase until the follow-up visit will be collected and reported to the Sponsor/CRO.

If a subject becomes pregnant from the beginning of the study treatment in the washout phase until the follow-up visit, she will be instructed to commence discontinuation of the study medication. Further, the subject (or female partner of a male subject) will be instructed to return promptly after the first notification of pregnancy to the study center and undergo a serum pregnancy test, as confirmation of pregnancy. If positive, the subject will no longer receive any additional study medication. All pregnancies will be followed until resolution (ie, termination [voluntary or spontaneous] or birth). If the Investigator becomes aware of pregnancies, this must be promptly reported directly or by telephone or facsimile to the Sponsor/CRO (Table 1 and 2 Emergency Contact Information). The Investigator must complete the Pregnancy Event Form and send it to the Sponsor/CRO.

Pregnancy itself is not regarded as an AE unless there is a suspicion that the study drug may have interfered with the effectiveness of a contraceptive medication or other AEs

were detected.

### **13. TERMINATION OF SUBJECT FROM STUDY/DISCONTINUATION OF STUDY DRUG**

#### **13.1 Criteria for Subject Termination**

Subjects may terminate the study participation at any time for any reason.

The possible reasons for the termination of study participation are as follows:

- Adverse event
- Suicide ideation
- Study drug discontinuation
- Lack of efficacy
- Lost to follow-up
- Pregnancy
- Withdrawal by subject
- Failure to apply >50% of the study medication since the last visit
- Protocol violation
- Other

If at any time during the course of the study, in the opinion of the Investigator, the subject may no longer safely participate due to a change in medical status (eg, experiences an AE or suicide ideation, becomes pregnant), or discontinuation of the study drug should be considered, the subject must be discontinued from the study treatment.

The date of discontinuation and the reason for discontinuation will be recorded in the appropriate CRF. Subjects who prematurely terminate the study participation will not be replaced.

#### **13.2 Clinical Assessments after Study Drug Discontinuation**

Every effort should be made for all randomized subjects prematurely discontinuing the study drug, regardless of cause, to undergo final evaluation procedures, in accordance with the discontinuation visit and the follow-up visit as described in Table 4 Schedule of Assessments for outside Japan (p11) or Table 5 Schedule of Assessments for Japan (p13). The subject will undergo the discontinuation assessments within 5 days of the last study drug application. However, if a subject completes the double-blind treatment

phase and discontinues before entering the open-label treatment phase, the subject will undergo the follow-up visit in Table 4 or that in Table 5.

Subjects with study drug application during the washout phase and prematurely discontinuing before randomization, will undergo the following safety assessments: study treatment compliance, skin irritation assessment, laboratory test, 12-lead ECG, body weight, body temperature, blood pressure, pulse rate, and adverse event monitoring at the discontinuation visit in Table 4 Schedule of Assessments for outside Japan (p11) or Table 5 Schedule of Assessments for Japan (p13).

### **13.3 Early Termination of the Study for Futility**

If the Sponsor decides early termination of the study for futility on the basis of the interim analysis, Investigators must stop obtaining consent from any new subjects and stop enrolling any subjects into the study. Investigators will inform all subjects already enrolled about the study termination. All subjects must be discontinued from the study treatment at any time during the course of the study and will undergo the clinical assessments described in Section 13.2 Clinical Assessments after Study Drug Discontinuation.

## **14. STUDY TERMINATION**

The Sponsor reserves the right to discontinue the study at multiple study centers for safety or administrative reasons at any time while ensuring that early termination does not compromise the safety or well-being of the subjects. In particular, a study center that does not recruit at an acceptable rate may be closed. Should the study be terminated and/or the study center closed for whatever reason, study medications pertaining to the study must be returned to the Sponsor/CRO.

If the Sponsor decides to prematurely terminate the study, the Sponsor will inform the Investigator and regulatory authorities of this termination and its reason, and in addition, the head of the study center in Japan must be informed. In the event of study or study center termination, the subjects will be provided with access to standard care.

### 15.1 Sample Size Determination

#### Double-blind treatment phase

The target number of randomized subjects is 501.

DSP-5423P 40 mg group	167
DSP-5423P 80 mg group	167
Placebo group	167

#### Rationale

The sample size for the study has already been determined by a Monte-Carlo simulation using Statistical Analysis Software (SAS Version 9.3, SAS Institute). The sample size calculation is based on the number of subjects required for the primary analysis in the modified intention-to-treat (mITT) population, wherein the primary analysis is to be performed on the change in PANSS total score from baseline at

Week 6. The Hochberg procedure will be utilized for the multiplicity adjustment to the multiple comparisons between each DSP-5423P (40 and 80 mg/day) group and the placebo group. Neither a placebo-controlled study nor an active-controlled study of DSP-5423P has been conducted. In contrast, a double-blind placebo-controlled study of DSP-5423 (tablets, 2.5, 5 and 10 mg/day) treatment for 6 weeks for comparison with the placebo has been conductedref.16. The results of the study are shown in Table 16. The sample size for the study has been determined on the basis of the effect size estimated using the result of each DSP-5423 group except DSP-5423 2.5 mg/day in this study because DSP-5423P doses in the study were chosen to correspond to DSP-5423 8 and 16 mg/day.

**Table 16 Change in PANSS total score**

Treatment group	N	Change in PANSS total score from baseline	
		Mean ± SD	Effect Size (95% CI)
DSP-5423 2.5 mg	60	-20.433±21.101	-0.338 (-0.689, 0.021)
DSP-5423 5 mg	57	-27.123±17.461	-0.650 (-1.020, -0.279)
DSP-5423 10 mg	62	-29.516±24.721	-0.667 (-1.030, -0.304)
HPD 10 mg	58	-27.569±17.623	-0.669 (-1.038, -0.299)
Placebo	61	-12.213±26.840	-

Abbreviation: HPD=haloperidol

The effect sizeref.17 was estimated to be 0.650 for DSP-5423 5 mg/day and 0.667 for DSP-5423 10 mg/day based on this study. It is considered that the change in PANSS total score from baseline will be smaller than in past study because in the earlier study, in which the enrollment criteria targeted outpatients or inpatients hospitalized within two weeks according to acute aggravation, more patients with a newly exacerbated psychotic state were enrolled than in this study. In addition, a trend for drug-placebo differences in the clinical trial to be diminishing annually in the field of schizophrenia has been pointed outref.18. For the reasons noted above, the effect size in the present study is assumed to be 0.45 which is about two-thirds of the effect size of DSP-5423 5 mg/day and DSP-5423 10 mg/day. A sample size of 133 per group was estimated to yield a complete power (probability of rejecting 2 null hypotheses) of 89% with a two-sided 5% significance level using the Hochberg procedure for multiplicity adjustment and taking an interim analysis for futility into consideration. Considering that there is the possibility of subjects discontinuing before completion of the double-blind treatment phase, the total sample size will need to be 501 subjects or 167 subjects per treatment group.

## **15.2 Analysis Populations**

The primary efficacy analysis will be performed in the modified intention-to-treat (mITT) population. The efficacy analysis on the primary variable will also be performed in the per-protocol (PP) population for sensitivity analysis. Some efficacy data in the open-label treatment phase will be analyzed for the open-label treatment phase population. The safety analysis will be performed in the safety population. Efficacy and safety analyses for DSP-5423P treatment period will be performed on DSP-5423P dosed population. The mITT analysis will be performed using the assigned treatment groups, and the safety analysis using the groups of the treatment actually received.

### **15.2.1 Modified intention-to-treat population (mITT population)**

The mITT population will consist of all subjects who meet all the following:

- Subjects who are randomized and apply the study drug at least once in the double-blind treatment phase.
- Subjects who have baseline and at least one post-baseline PANSS total score rated in the double-blind treatment phase.

### **15.2.2 Per-protocol population (PP population)**

The PP population will consist of subjects of the mITT population who meet all the following:

- Subjects who meet the inclusion criteria at screening (1) to (4), and (7) and do not meet any of the exclusion criteria at screening (12) to (17), and (22)
- Subjects who meet all of the inclusion criteria at randomization and do not meet the exclusion criterion at randomization (1)
- Subjects who apply at least 80% of the study treatment in the double-blind treatment phase
- Subjects who receive no antipsychotics during the washout phase and the double-blind treatment phase.
- Subjects who have no other important protocol deviations with an impact on the efficacy analyses as determined by a blinded data review

### **15.2.3 Open-label population**

The open-label population will consist of all subjects who apply DSP-5423P at least once in the open-label treatment phase.

#### **15.2.4 Safety population**

The safety population will consist of all subjects who are randomized and apply the study drug at least once during the study.

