#### **For the washout phase and the double-blind treatment phase**

The study drugs for the washout phase and the double-blind treatment phase will be packaged in paper boxes with uniquely identifiable numbers, ie, a Kit ID. A paper box contains 7 plastic bags for 7-day treatments. The packaging contains 2 aluminum-laminated patches in a plastic bag (1 patch in each laminate).

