### **10.1 Study Medication**

The study drug (patches) will be applied to the subject's back, chest, or abdomen once daily around the same time of the day from the beginning of the washout phase until the end of the open-label treatment phase. All patches for each day should be applied to only one location, ie, the back, the chest, or the abdomen. The study drug will be replaced every day. When the study drug patches are to be replaced, the new patches will be applied to the location different from that of the last application, or a site different from that of the last application on the same location.

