5.4 Safety population

The safety population will consist of all subjects who are randomized and apply the study drug at least once during the study.

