7.2 Subject Disposition and Data Sets Analyzed

Subject disposition will be listed and summarized by treatment group and overall, and will include the number and percentage of subjects for the double-blind treatment phase and the open-label treatment phase, the denominator of the percentage will be the number of randomized subjects and the number of the open-label population, respectively. Summaries of subject disposition will be repeated by country for both treatment phases.

For the double-blind treatment phase, the following information will be reported:

- informed consent obtained,
- not enrolled in the wash-out phase; with breakdown by reason for disposition,
- enrolled in the wash-out phase,
- not randomized; with breakdown by reason for disposition,
- randomized,

Statistical Analysis Plan

Version: 2

Study No. D4904020

- not treated in the double-blind treatment phase; with breakdown by reason for disposition,
- treated in the double-blind treatment phase,
- completed the double-blind treatment phase,
- discontinued from the double-blind treatment phase; with breakdown by reason for disposition.

For the open-label treatment phase, the following information will be reported:

- completed the double-blind treatment phase,
- not treated in the open-label treatment phase; with breakdown by reason for disposition,
- treated in the open-label treatment phase,
- Ongoing; displayed ONLY for interim data analysis,
- completed the open-label treatment phase,
- discontinued from the open-label treatment phase; with breakdown by reason for disposition.

The number and percentage of subjects who included in each analysis population will be summarized for the double-blind treatment phase and the open-label treatment phase, where the denominator of the percentage will be the number of randomized subjects and the number of subject treated at least once in the open-label treatment phase, respectively. These summaries will be repeated by country.

For the double-blind treatment phase, the following analysis populations are of interest:

- mITT population,
- PP population,
- Safety population,
- PK population.

For the open-label treatment phase, the following analysis populations are of interest:

- Open-label population,
- DSP-5423P dosed population,
- PK population.

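### The safety population's exposure condition is already met by washout placebo, so randomized subjects never treated in the double-blind phase stay in the safety denominators

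*Protocol*

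**What the plan says.** Protocol 15.2.4 includes "all subjects who are randomized and apply the study drug at least once during the study". SAP 5.4 uses the same condition, "randomized and apply the study drug at least once during the study", and names no phase. The mITT definition in Protocol 15.2.1 (and SAP 5.1) does name one: "Subjects who are randomized and apply the study drug at least once in the double-blind treatment phase".

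The protocol's use of the term study drug covers the washout patches:

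- Section 10.1 has it applied "once daily around the same time of the day from the beginning of the washout phase until the end of the open-label treatment phase".
- Section 9.2.1 states: "The study drugs for the washout phase and the double-blind treatment phase will be packaged in paper boxes".
- Section 13.2 speaks of "Subjects with study drug application during the washout phase and prematurely discontinuing before randomization".
- Section 9.1 and Table 7 list the placebo patch as one of the study drugs, and section 7.1 counts washout among the four phases of the study.

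Both documents provide for randomized subjects who get no double-blind treatment. Protocol 15.3.1 counts them, and SAP 7.2 has the line "not treated in the double-blind treatment phase; with breakdown by reason for disposition". On grouping, Protocol 15.2 specifies "the safety analysis using the groups of the treatment actually received".

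**The concern.** A safety set normally requires exposure so that its denominators hold only subjects who could show an effect of the treatment being compared. Here washout placebo satisfies the requirement before randomization, so it removes almost nobody. The subjects it ought to remove are those with no double-blind application, and the double-blind safety rules are not built for them.

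At stake are the placebo-controlled safety percentages, which serve the secondary objective in Protocol 5.2. If the definition is followed as written, those percentages carry subjects who were never exposed to any randomized treatment.

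**Working it through.** There is no stated figure to reproduce, because the point concerns a definition. The check has three steps.

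**1. Who meets the condition.** Washout placebo is worn for at least 3 days before randomization (Protocol 7.1, 10.1.1). A randomized subject who followed the protocol has therefore applied study drug during the study. Open-label entry requires completion of the 6-week double-blind treatment (Protocol 8.3.1). So a subject with some application during the study but none in the double-blind phase can only have had washout placebo. Those are exactly the subjects by whom the safety wording and a phase-limited wording differ.

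**2. What such a subject contributes.**

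| Rule | Where | Result for a subject with no double-blind application |
|---|---|---|
| Day 1 is the first double-blind application | Protocol 15.3.8.1, SAP 6.1 | No Day 1 |
| Double-blind TEAE starts on or after that date | Protocol 15.3.6.1, SAP 7.7.1 | No dated event qualifies |
| AE whose start date is still missing or incomplete after imputation counts as a TEAE | SAP 7.7.1, with 6.5.1 | The one route to an event |
| Post-baseline data run from Day 1 | SAP 6.3 | None |
| Compliance and exposure use double-blind application dates | SAP 7.5, 7.5.1 | Missing |

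The subject is counted in the denominator and, with the one exception, nowhere else.

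**3. Size.** The documents give no number of such subjects, so this part is an illustration under assumptions. Let N be the subjects randomized per arm, u the share of each arm left untreated (equal across arms), k = uN, and r the TEAE rate among treated subjects. Untreated subjects are taken to have no TEAEs.

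- Grouped by treatment received, with washout placebo counted as placebo: the placebo denominator is (N − k) + 3k = N + 2k, and its rate is r(N − k)/(N + 2k) = r(1 − u)/(1 + 2u). Each active arm has denominator N − k and keeps rate r.
- Grouped as randomized: every arm has rate r(N − k)/N = r(1 − u).

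With N = 167 (Protocol 15.1) and r = 60%:

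| u | k per arm | Placebo denominator N + 2k | Placebo rate, by treatment received | Every arm, as randomized |
|---|---|---|---|---|
| 0.5% | 0.8 | 168.7 | 99.7/168.7 = 59.1% | 59.7% |
| 1% | 1.7 | 170.3 | 99.2/170.3 = 58.2% | 59.4% |
| 2% | 3.3 | 173.7 | 98.2/173.7 = 56.5% | 58.8% |

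The counts are expected values and so need not be whole. With r = 30%, placebo reads 29.6%, 29.1% and 28.3% by treatment received, and every arm 29.9%, 29.7% and 29.4% as randomized. N cancels from both rates, so the 582 subjects randomized according to SAP Appendix II (194 per arm if equal) give the same percentages.

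**The case against.** A reader might infer that these subjects will be counted as placebo and will bias the comparison in one direction. The documents do not go that far. Protocol 15.2 calls for grouping by treatment received, but no text assigns an untreated subject to placebo. Protocol 10.7.1 lists three randomized treatments, and single-blind washout placebo, worn by everyone, is not one of them. The SAP does not repeat the rule, and its mock safety code in 7.7.5 groups by trt01p, a name that suggests planned treatment. Grouped that way, the dilution is shared by all arms. Even if they were moved to placebo, the active arms would look relatively worse, so the wording does not hide a drug risk.

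It is also tempting to say that such subjects cannot have a TEAE. The missing-start-date rule in SAP 7.7.1 makes that too absolute.

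Other SAP text suggests that the narrower meaning was intended. Section 7.2 lists the safety population under the double-blind phase. Section 7.4.3, in defining prior medications, equates the initial dose of study medication with the first double-blind application. Sections 7.5 and 7.5.1 ask for summaries on the safety population that an untreated subject cannot supply.

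Finally, numbers should be few. Randomization and dispensing both happen at Visit 2, within Day -2 to Day 1, and subjects are inpatients until Day 14. SAP 7.7.1 plans no statistical comparison of AEs, and the DIEPSS models use only post-baseline data.

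All of this limits the consequences, and it stands. None of it changes the definition in Protocol 15.2.4 or SAP 5.4.

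**Conclusion.** The wording defect is real and minor. As written, the exposure condition excludes essentially no randomized subject, and any subject untreated in the double-blind phase inflates the safety denominators. The direction of the distortion is open, because the documents do not settle how such a subject is grouped. A claim that placebo rates will be biased downward relative to drug is therefore not supported; it is one of two possible outcomes.

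Under the assumed 0.5% to 2% untreated and a 60% TEAE rate, the shift is 0.9 to 3.5 percentage points in placebo alone, or 0.3 to 1.2 points in every arm. The untreated share and the event rate are assumptions. If every randomized subject is treated, the effect is nil. No planned significance test is shown to be affected.

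**What to change.** In Protocol 15.2.4 and SAP 5.4, replace the closing words *during the study* with *in the double-blind treatment phase*, matching the mITT definition. This aligns the safety set with the TEAE, exposure and compliance rules, all of which start at the first double-blind application. Nothing is lost for later data, since the open-label and DSP-5423P treatment-period summaries have their own populations.

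It would also help to add one sentence to the SAP saying how the actual-treatment group is derived for safety tables, because the protocol's rule is not carried over there.

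The cost is a few words in each document. No data collection, sample size or efficacy analysis changes.
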